5.3. Additional Eligibility Criteria

To assess any potential impact on participant eligibility with regard to safety, the investigator must refer to the IB and supplements, approved product labels, and/or local prescribing information for detailed information regarding warnings, precautions, contraindications, AEs, drug interactions, and other significant data pertaining to the study drugs.

Notwithstanding these minimum inclusion and exclusion criteria, investigators must also follow country specific guidelines where they exist when making decisions about participants who are eligible for study participation.

5.4. Screening/Baseline/Run-in Failures

Screen failures are defined as participants who consent to participate in the clinical trial but are never subsequently randomized. In order to ensure transparent reporting of screen failure participants, meet the Consolidated Standards of Reporting Trials (CONSORT) publishing requirements, and respond to queries from Regulatory authorities, a minimal set of screen failure information is required including Demography, Screen Failure details, Eligibility Criteria, and Serious Adverse Events.

A single repeat of a procedure / lab parameter is allowed to determine eligibility (unless otherwise specified).

Participants are allowed to re-screen for this study one time. This will require a new participant number.

5.5. Withdrawal/Stopping Criteria

Participants permanently discontinuing study treatments prior to the Week 100 visit are considered to be withdrawn from the study treatments. Participants who enter the Extension Phase but permanently discontinue participation in the Extension Phase prior to commercially available CAB LA + RPV LA are considered to be withdrawn from the study treatments but are not considered to be withdrawn from the study because they will enter the follow Follow-up Phase.

A participant may withdraw consent and discontinue participation in this study at any time at his/her own request. The investigator may also, at his or her discretion, discontinue the participant from participating in this study at any time (e.g., safety, behavioral or administrative reasons). Participants may have a temporary interruption to their study treatment for management of toxicities. If a participant withdraws from the study, he/she may request destruction of any samples taken, and the investigator must document this in the site study records. Withdrawn participants will not be replaced.

All participants who discontinue prematurely from the study, irrespective of arm, will be asked for additional information to establish the reason for withdrawal.

Participants are not obligated to state the reason for withdrawal. However, the reasons for withdrawal, or failure to provide a reason, must be documented by the Investigator on the Completion/Withdrawal section of the electronic case report form (eCRF). Every effort should be made by the Investigator to follow-up participants who withdraw from the study.

A in-clinic withdrawal visit will also be used to assess participants with ongoing AEs, and serious adverse events (SAEs) related & not related to study drug and also any laboratory abnormalities that are considered to be AEs or potentially harmful to the participant. The withdrawal visit will be distinct from visits conducted during the LTFU Phase.

Following completion of withdrawal assessments, all participants who received one or more injections of CAB LA+ RPV LA will subsequently enter the LTFU Phase initiating with the Month 3 LTFU visit.

Withdrawal decision coincides with a planned clinic visit:

- For any participant who withdraws prematurely from the Maintenance or Extension Phase during a planned in-clinic study visit, withdrawal assessments and procedures are to be performed (according to the Time and Events Table (Section 7.1) instead of the assessments for the active planned visit during which the withdrawal decision is made.

Withdrawal decision occurs between planned clinic visits:

- In the event that a decision to withdraw a participant occurs between clinic visits, participants will be instructed to return for an unscheduled withdrawal visit (within 4 weeks of the last Q4W LA injection or within 8 weeks of the last Q8W LA injection received) during which withdrawal assessments according to the Time and Events Table (Section 7.1) will be completed. For participants who received one or more injections of CAB LA+ RPV LA **withdrawal assessments must occur prior to initiation of the next ART regimen.**

If withdrawal coincides with the active planned Week 52 or Week 100 visits, HIV-1 RNA will only be assessed if the last HIV-RNA measurement from Week 48 or Week 96 was ≥ 50 copies per mL (i.e. retest for viral load blip). This will ensure that only the Week 48 or Week 96 viral load assessments or required retest will be counted towards the primary and secondary efficacy endpoint windows.

The in-clinic visit will be recorded as an unscheduled withdrawal visit with the following exception. A withdrawal visit and assessments coinciding with the planned Week 100 visit will be recorded as the Week 100 visit such that the participant can be considered a completer, consistent with the definition of study completer in Section 5.6.

Participants may be prematurely discontinued from the study treatment for any of the following reasons:

- Adverse event / Serious adverse event
- Protocol deviation
- Intolerability of injections
- Participant lost to follow-up
- Participant or Investigator non-compliance;
- Termination of the study by the Sponsor
- At the request of the participant, Investigator, GSK or ViiV Healthcare;

- The participant requires concurrent prohibited medications during the course of the study. The participant may remain in the study if in the opinion of the Investigator and the medical monitor; such medication will not interfere with the conduct or interpretation of the study or compromise the safety of the participant.

Participants must be discontinued from study treatment for any of the following reasons:

- Participants who are not eligible to continue into the Maintenance Phase.
- Participants who are not eligible, or do not wish to continue on to the Extension Phase.
- Virologic withdrawal criteria as specified in Section 5.5.4 are met;
- Participant requires substitution of ART;
- Participant requires substitution or dose reduction of CAB LA or RPV LA (oral bridging supply and potential for a second loading dose may be permissible following discussion with the Medical Monitor).
- Liver toxicity where stopping criteria are met and no compelling alternate cause is identified (see Section 5.5.1);
- Renal toxicity are met and no compelling alternate cause is identified;
- QT interval (QTc) interval >550 msec from three or more tracings separated by at least 5 minutes and considered causally related to IP.
- Grade 4 clinical AE considered causally related to study drug;
- Participant has a Grade 3 or higher rash or Grade 2 rash with evidence of systemic involvement and no compelling alternative cause is identified
- Pregnancy (intrauterine), regardless of termination status of pregnancy.
- Participant withdrew consent

Efficacy data for participants withdrawing from the study will be considered evaluable up to the point at which they are withdrawn using the same criteria for evaluability as for participants who complete the study.

Safety data for all participants who receive any amount of study drug, including participants who withdraw from the study, will be included in evaluations of safety.

All data from the Withdrawal visit will be recorded, as they comprise an essential evaluation that should be done prior to discharging any participant from the study.

The following actions must be taken in relation to a participant who fails to attend the clinic for a required study visit:

- a. The site must attempt to contact the participant and re-schedule the missed visit as soon as possible.

- b. The site must counsel the participant on the importance of maintaining the assigned visit schedule and ascertain whether or not the participant wishes to and/or should continue in the study.
- c. In cases where the participant is deemed 'lost to follow up', the investigator or designee must make every effort to regain contact with the participant (where possible, 3 telephone calls and if necessary a certified letter to the participant's last known mailing address or local equivalent methods). These contact attempts should be documented in the participant's medical record.
- d. Should the participant continue to be unreachable, only then will he/she be considered to have withdrawn from the study with a primary reason of "Lost to Follow-up".

A participant may withdraw from study treatment at any time at his/her own request, or may be withdrawn at any time at the discretion of the investigator for safety, behavioral or administrative reasons. If a participant withdraws from the study, he/she may request destruction of any samples taken, and the investigator must document this in the site study records.

5.5.1. Liver Chemistry Stopping Criteria

Liver chemistry stopping and increased monitoring criteria have been designed to assure participant safety and evaluate liver event etiology.

IP will be stopped if any of the following liver chemistry criteria are met:

- ALT ≥ 3 xULN and bilirubin ≥ 2 xULN (>35% direct bilirubin, bilirubin fractionation required).
- NOTE: serum bilirubin fractionation should be performed if testing is available. If testing is unavailable, sites should evaluate the presence of detectable urinary bilirubin on dipstick, indicating direct bilirubin elevations and suggesting liver injury. If testing is unavailable and a participant meets the criterion of total bilirubin ≥ 2 xULN, then the event meets liver stopping criteria.
- ALT ≥ 8 xULN.
- ALT ≥ 3 xULN (if Baseline ALT is <ULN) with symptoms or worsening of acute hepatitis or hypersensitivity such as fatigue, nausea, vomiting, right upper quadrant pain or tenderness, fever, rash, or eosinophilia, OR;
- ALT ≥ 3 x Baseline ALT with symptoms or worsening of acute hepatitis or hypersensitivity such as fatigue, nausea, vomiting, right upper quadrant pain or tenderness, fever, rash, or eosinophilia;
- ALT ≥ 5 xULN and <8xULN that persists ≥ 2 weeks (with bilirubin <2 ULN & no signs or symptoms of acute hepatitis or hypersensitivity).
- ALT ≥ 5 xULN but <8xULN and cannot be monitored weekly for >2 weeks.

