5.5.1.1. Liver Chemistry Stopping Criteria, Participant Management and Follow-Up

Participants who develop ALT $\geq 5 \times \text{ULN}$ must be followed weekly until resolution or stabilization (ALT $< 5 \times \text{ULN}$ on 2 consecutive evaluations).

When any of the liver chemistry stopping criteria is met, do the following:

- Immediately hold IP. If on LA therapy, **do not** administer another injection until approval is received from the ViiV Safety and Labelling Committee.
- Report the event to the Medical Monitor within 24 hours of learning its occurrence.
- Complete the liver event eCRF and SAE eCRF, where applicable.
- Complete the liver imaging and/or liver biopsy eCRFs if these tests are performed.
- Perform liver event follow up assessments (described below), and monitor the participant until liver chemistries resolve, stabilize, or return to Baseline values as described below.
- Make every reasonable attempt to have participants return to clinic within 24 hours for repeat liver chemistries, liver event follow-up assessments (see below), and close monitoring.
- A specialist or hepatology consultation is recommended.
- Monitor participants twice weekly until liver chemistries (ALT, AST, alkaline phosphatase, bilirubin) resolve, stabilize or return to within Baseline values.

Make every attempt to carry out the **liver event follow-up assessments** described below:

- Viral hepatitis serology including:
 - Hepatitis A immunoglobulin M (IgM) antibody;
 - Hepatitis B surface antigen (HBsAg) and Hepatitis B Core Antibody (IgM);
 - Hepatitis C RNA;
 - Hepatitis E IgM antibody;
 - Cytomegalovirus IgM antibody;
 - Epstein-Barr viral capsid antigen IgM antibody (or if unavailable, obtain heterophile antibody or monospot testing);
- Syphilis screening;
- Drugs of abuse screen including alcohol;
- Serum acetaminophen test (N-acetyl-para-aminophenol [APAP] adduct test). The site must contact GSK when this test is required. Please refer to the central laboratory manual.
- Blood sample for pharmacokinetic (PK) analysis, obtained during follow up assessments. Record the date/time of the PK blood sample draw and the date/time of

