5.5.1.3. Liver Chemistry Stopping Criteria – Restart / Rechallenge

Participants who meet liver toxicity stopping criteria should not be retreated with investigational product unless an exemption has been approved by the ViiV Safety and Labeling Committee (VSLC). The guideline for Restart /Rechallenge approved by the VSLC, which is maintained as a separate document must be followed.

5.5.1.3.1. Drug Restart / Rechallenge. Following Liver Events that are Possibly Related to IP

- Approval by the VSLC for drug restart or additional IM administration can be considered where:
- The participant is receiving compelling benefit, benefit of drug restart exceeds risk, and no effective alternative therapy is available. Ethics Committee or Institutional Review Board approval of drug restart / rechallenge must be obtained, as required.

- If the restart / rechallenge is approved by the VSLC in writing, the participant must be provided with a clear description of the possible benefits and risks of drug administration, including the possibility of recurrent, more severe liver injury or death.
- The participant must also provide signed informed consent specifically for the IP restart / rechallenge. Documentation of informed consent must be recorded in the study chart.
- Study drug must be administered at the dose specified by the VSLC.
- Participants approved by the VSLC for rechallenge of IP must return to the clinic twice a week for liver chemistry tests for a minimum of one month and thereafter for as long as clinically indicated and then laboratory monitoring may resume as per protocol. If protocol defined stopping criteria for liver chemistry elevations are met, study drug must be stopped.

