6.9.1. IM Dosing

Participants receiving CAB LA and/or RPV LA are anticipated to be at risk for development of virologic resistance if ART is interrupted. The time period during which participants are at risk for development of virologic resistance may be determined by the period between when drug levels fall below therapeutic values and when they fall below levels which exert selective pressure on HIV. This time period will vary by ART agent and is dependent upon effective concentration, inhibitory concentration, and half-life.

Plasma concentrations of both LA drugs may be measurable for more than one year following IM injections. Any interruption in IM dosing should be discussed with the Medical Monitor. Investigators should ensure that the participant initiates alternative highly active ART to minimize the risk of developing resistance as concentrations of CAB and RPV decline over time.

IM dosing is expected to occur during the week in which the participant's projected visit falls (as according to the date of the first injection). The first injections for participants from ATLAS on CAB LA + RPV LA Q4W will occur at Day 1. The first injections for participants transitioning from oral SOC are administered at Week 4b (can be performed as soon as lab results from Week 4a become available and should be performed where possible within 2 weeks of visit 4a), and the second injections are given at Week 8. Between the Week 4a and 4b visits, participants must continue daily treatment with oral CAB and RPV tablets.

Since the first injection visit (Day 1 or 4b) will determine the future injection visit schedule for participants, planning for the first injection visit date (within allowed visit windows) should take into consideration the availability of the participants to adhere to future visit windows (planned vacations, business trips, *etc.*).

CAB LA + RPV LA dosing for participants transitioning from SOC treatment is as follows:

All injections should be planned as single injections per drug.

6.9.1.1. IM injections every 4 weeks (Q4W):

Week 4b only - CAB LA 600 mg + RPV LA 900 mg, each given as 1 X 3 mL IM injection

Week 8 and Q4W thereafter - CAB LA 400 mg IM + RPV LA 600 mg IM every 4 weeks for 100 weeks, each given as 1 X 2 mL IM injection

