7.4.3.4. Prompt Reporting of Serious Adverse Events and Other Events

SAEs, pregnancies, and liver function abnormalities meeting pre-defined criteria will be reported promptly by the investigator to the medical monitor as described in Table 9 once the investigator determines that the event meets the protocol definition for that event. Any seizure or suspected seizure should be reported in an expedited manner, as noted in Table 9.

Criteria for liver chemistry stopping and follow-up criteria are in Section 5.5.1.

Table 9 Reporting of Serious Adverse Events and Other Events

Type of Event	Initial Reports		Follow-up Information on a Previous Report	
	Time Frame	Documents	Time Frame	Documents
All SAEs	24 hours	“SAE” data collection tool	24 hours	Updated “SAE” data collection tool
Cardiovascular or death event	Initial and follow-up reports to be completed when the cardiovascular event or death is reported ^a	“CV events” and/or “death” data collection tool(s) if applicable	Initial and follow-up reports to be completed when the cardiovascular event or death is reported ^a	Updated “CV events” and/or “death” data collection tool(s) if applicable
Pregnancy	24 hours	“Pregnancy Notification Form”	Within 24 hours of investigator awareness of pregnancy outcome	“Pregnancy Follow-up Form” and SAE if required
Seizure or suspected seizure	24 hours	eCRF	24 hours	eCRF
Suspected ABC HSR in participants receiving Oral SOC during the Long-Term Follow-Up Phase ^b	1 week	ABC HSR eCRF	1 week	Updated ABC HSR eCRF
ALT \geq 3 \times ULN and bilirubin \geq 2 \times ULN (>35% direct) (or ALT \geq 3 \times ULN)	24 hours ^c	“SAE” data collection tool. “Liver Event eCRF” and “Liver Imaging” and/or “Liver Biopsy” eCRFs, if applicable ^d	24 hours	Updated “SAE” data collection tool/“Liver Event” documents ^d
ALT \geq 5 \times ULN that persists \geq 2 weeks	24 hours ^c	Liver Event eCRF ^d	24 hours	Updated Liver Event eCRF ^d
ALT \geq 8 \times ULN	24 hours ^c	Liver Event eCRF ^d	24 hours	Updated Liver Event eCRF ^d
ALT \geq 3 \times ULN (if baseline ALT is <ULN) or ALT \geq 3 fold increase from baseline value with appearance or worsening of symptoms of hepatitis or hypersensitivity	24 hours ^c	Liver Event eCRF ^d	24 hours	Updated Liver Event eCRF ^d

- Additional details and time frames for reporting supplementary information for cardiovascular and death events are provided in Section 7.4.3.7 and Section 7.4.3.8, respectively.

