7.4.4.3. Grade 3 Toxicity/Adverse Event

Participants who develop a Grade 3 AE or toxicity should be managed as follows:

- If the Investigator has compelling evidence that the Grade 3 AE or toxicity has not been caused by IP, dosing may continue after discussion with the Medical Monitor.
- Participants who develop a Grade 3 AE or toxicity, which the Investigator considers related or possibly related to the IP, should have the IP withheld and be rechecked each week until the AE returns to Grade 2. Once the AE is Grade \leq 2, IP may be re-started.
- Should the same Grade 3 AE recur within 28 days in the same participant, the IP should be permanently discontinued and the participant withdrawn from study.
- Participants experiencing Grade 3 AEs requiring permanent discontinuation of IP should be followed weekly until resolution of the AE and to have withdrawal study evaluations completed. A follow-up visit should be performed 4 weeks after the last dose of IP. Any participant receiving at least one dose of CAB LA and /or RPV LA who discontinue IP / Withdraw will initiate treatment with HAART and enter the LTFU Phase for 52 weeks of follow up.

- Participants with Grade 3 asymptomatic laboratory abnormalities should be investigated for all potential non-drug related causes, and, following discussion with the Medical Monitor, may continue IP if the Investigator has compelling evidence that the toxicity is not related to IP, with the exception of liver chemistry stopping criteria (See Section 7.4.5.1). Isolated Grade 3 lipid abnormalities do not require withdrawal of IP.

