7.4.5.1. Liver Chemistry Stopping and Follow-up Criteria

Liver chemistry threshold stopping criteria have been designed to assure participant safety and to evaluate liver event etiology during administration of study drug and the follow-up phase. All Phase 3 participants who meet liver stopping criteria will be adjudicated by the ViiV Safety and Labelling Committee (VSLC) – resulting in a case summary, adjudication, and management plan. The VSLC contains an external expert hepatologist, familiar with both DILI and cabotegravir, who will participate in this review. This committee meets on a 3-weekly basis, and can be convened on an ad hoc basis as needed.

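### Liver stopping rule, Section 5.5.1, fifth criterion: raised bilirubin or symptoms can remove a stop that the same persistent ALT of 5 to <8×ULN would otherwise trigger

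*Protocol*

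**What the plan says.** Section 5.5.1 stops IP if any of six criteria is met:

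1. ALT ≥3×ULN with bilirubin ≥2×ULN, more than 35% direct. If neither fractionation nor the urine dipstick is available, total bilirubin ≥2×ULN is enough.
2. ALT ≥8×ULN.
3. ALT ≥3×ULN with symptoms, if baseline ALT is below ULN.
4. ALT ≥3 times baseline, with symptoms.
5. ALT ≥5 and <8×ULN for at least 2 weeks, "with bilirubin <2 ULN & no signs or symptoms of acute hepatitis or hypersensitivity".
6. ALT ≥5 and <8×ULN when weekly monitoring for more than 2 weeks is not possible.

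Other provisions depend on one of these being met:

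- Section 5.5.1.1 holds IP immediately and, on LA therapy, tells the site not to "administer another injection until approval is received from the ViiV Safety and Labelling Committee".
- Section 7.4.5.1 provides that "participants who meet liver stopping criteria will be adjudicated by the ViiV Safety and Labelling Committee".
- Section 5.5 requires discontinuation for "Liver toxicity where stopping criteria are met and no compelling alternate cause is identified".
- Under Section 5.5.1.3 such participants "should not be retreated with investigational product unless an exemption has been approved".

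Table 9 (Section 7.4.3.4) has a 24-hour reporting row for ALT ≥5×"ULN that persists" at least 2 weeks, with no bilirubin or symptom condition.

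**The concern.** The parenthesis reads as if bilirubin ≥2×ULN or symptoms would always be picked up by criteria 1, 3 or 4. Those criteria carry restrictions of their own, so some participants fall between them. Adding an abnormality to a persistent ALT of 5 to <8×ULN can then turn a stop into no stop. A safety rule should not work in that direction.

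The participants concerned can be enrolled. Exclusion criterion 33 bars only ALT ≥3×ULN. Criterion 19 admits asymptomatic chronic hepatitis C, and criterion 21 admits Gilbert's syndrome. Direct bilirubin is measured reflexively above 1.5×ULN (Table 8, footnote a), so the allowance for unavailable testing will not normally rescue group (a).

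The hold matters more than it would for a daily tablet, because an injection cannot be withdrawn. Section 6.9.1 says "Plasma concentrations of both LA drugs may be measurable for more than one year following IM injections".

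**Working it through.** The protocol gives no figure to reproduce; the check is logical. All values are multiples of ULN, ALT has persisted for at least 2 weeks and weekly monitoring is possible, so criterion 6 does not apply. ALT is below 8, so criterion 2 does not apply.

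**Group (a): no symptoms, bilirubin ≥2, at most 35% direct.** Example: ALT 6 for 4 weeks, bilirubin 2.5 at 20% direct.
- Criterion 1: needs more than 35% direct. Not met.
- Criteria 3 and 4: need symptoms. Not met.
- Criterion 5: needs bilirubin <2. Not met.
- The same participant with normal bilirubin meets criterion 5 and is stopped.

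Baseline ALT plays no part, so group (a) is missed at every baseline and every ALT from 5 to <8.

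**Group (b): symptoms, without bilirubin ≥2 at more than 35% direct.** Example: baseline 2, ALT 5.5 for 4 weeks, normal bilirubin, hepatitis symptoms.
- Criterion 1: not met.
- Criterion 3: needs baseline <1. Not met.
- Criterion 4: needs ALT ≥3 × 2 = 6. Not met.
- Criterion 5: needs no symptoms. Not met.
- The same participant without symptoms meets criterion 5 and is stopped.

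Group (b) is missed when ALT < 3 × baseline, that is, baseline > ALT/3:

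| ALT (×ULN) | Missed if baseline exceeds (×ULN) |
|---|---|
| 5 | 5/3 = 1.67 |
| 5.5 | 5.5/3 = 1.83 |
| 6 | 6/3 = 2.00 |
| 7 | 7/3 = 2.33 |
| 7.95 | 7.95/3 = 2.65 |

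For a baseline from 8/3 = 2.67 to <3, the whole band is missed.

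**Enumeration.** The six criteria were applied to ALT 5.00 to 7.95 (60 values) and baseline 0.20 to 2.95 (56 values) in steps of 0.05, giving 60 × 56 = 3,360 cells per row. These are logical combinations, not participant frequencies. Entries are cells stopped.

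| Symptoms | Bilirubin | As written | Bilirubin part deleted | Symptom part deleted | Whole parenthesis deleted |
|---|---|---|---|---|---|
| No | <2 | 3,360 | 3,360 | 3,360 | 3,360 |
| No | ≥2, >35% direct | 3,360 | 3,360 | 3,360 | 3,360 |
| No | ≥2, ≤35% direct | 0 | 3,360 | 0 | 3,360 |
| Yes | <2 | 2,390 | 2,390 | 3,360 | 3,360 |
| Yes | ≥2, >35% direct | 3,360 | 3,360 | 3,360 | 3,360 |
| Yes | ≥2, ≤35% direct | 2,390 | 2,390 | 2,390 | 3,360 |

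Each 2,390 row misses 3,360 − 2,390 = 970 cells; the lowest missed baseline on the grid is 1.70. Neither half-deletion closes both gaps.

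Over a wider grid (ALT 0.20 to 10.15, persistent or not, monitored weekly or not), deleting the whole parenthesis removes no existing stop. It adds 3,360 + 970 + 970 = 5,300 cells, all in groups (a) and (b).

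**The case against.** The strongest reply is that these participants are already managed, and from an earlier point. ALT of 5 to <10×ULN is Grade 3 (Appendix 2), and Section 7.4.4.3 withholds IP for a Grade 3 toxicity judged related or possibly related, without waiting 2 weeks. Section 7.4.4.2 requires Medical Monitor consultation at ALT ≥3×ULN before LA dosing continues. Weekly follow-up (Section 5.5.1.1), 24-hour reporting with sponsor contact (Table 9) and withdrawal for suspected drug-induced liver injury (Section 2.3.1) also apply. Sections 7.4.5.11 and 7.4.5.13 catch some symptomatic cases through allergic reaction or rash.

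This stands as mitigation, and it weakens any claim that mandatory discontinuation is wholly lost, because Section 2.3.1 applies a similar test. It does not replace the stopping rule. Withholding under Section 7.4.4.3 turns on the investigator's view of relatedness, and IP may be restarted at Grade ≤2 without the committee. For an asymptomatic laboratory abnormality, IP may continue after Medical Monitor discussion on "compelling evidence that the toxicity is not related to IP, with the exception of liver chemistry stopping criteria". That exception cannot operate here, because no criterion is met.

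Two further points are fair. Table 9 is a reporting table, and reporting more widely than stopping is not a contradiction; it shows only that the unrestricted trigger is already in use. And bilirubin that is mostly indirect, as in Gilbert's syndrome, is weak evidence of liver injury, which is why criterion 1 screens it out. But it gives no reason to exempt an ALT that criterion 5 treats as sufficient on its own.

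**Conclusion.** The concern holds. As written, criterion 5 stops a participant with persistent ALT of 5 to <8×ULN and no other abnormality, yet misses two enrollable groups with the same ALT and something more. Group (a) is missed throughout the band; group (b) is missed whenever baseline exceeds one third of current ALT, which requires a baseline above 1.67×ULN.

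This assumes that weekly monitoring is possible and that bilirubin fractionation is available; otherwise criterion 6, or the note to criterion 1, applies. Each group needs several conditions at once, and the protocol gives no basis for a frequency. The loss is the automatic hold pending committee approval, the adjudication and the retreatment bar, not all oversight. It is a safety-rule defect that should be corrected, with no claimed effect on any analysis or efficacy endpoint.

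**What to change.** Delete the parenthesis, so that criterion 5 applies to ALT ≥5 and <8×ULN persisting for at least 2 weeks, whatever the bilirubin or symptoms. Leave criterion 4 and Table 9 unchanged.

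The cost is one wording change in Section 5.5.1, no new scheduled tests or visits, and some additional holds, each with the Section 5.5.1.1 work-up. A hold on LA therapy also means arranging alternative ART to limit resistance (Section 6.9.1). Gilbert's syndrome alone would not justify restart under Section 5.5.1.3.2, because it explains the bilirubin and not the ALT. That route needs a clear cause for the liver event and recovery to ALT <3×ULN; otherwise the stricter Section 5.5.1.3.1 applies.
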